10.9 Data or Specimen Storage/Security

Data will be stored on an encrypted password protected laptop computer without any HIPAA identifiers. Strict confidentiality will be maintained in all records of the study by identifying subjects by code numbers. Information that is obtained in connection with this study and that can be identified with a subject will be kept confidential (subject's charts are kept in a locked room and file cabinet. Files will be kept in locked cabinets in a security system protected office. All information obtained from subjects is referred to by code number and kept in locked confidential files (subjects' paper charts are kept in an area protected with a security system, in a locked room and file cabinet). Any published results are published as group data without the use of characteristics that would identify individual subjects. We quote information only by number in conference discussions, scientific reports or publications to maintain anonymity.

Study data will periodically submitted to NIH National Data Archive (NDA; https://nda.nih.gov/). Grant recipients must include language in the informed consent form, agreeing that data and supporting documentation submitted to NDA may be accessed and used broadly by approved users for research. This submitted data is de-identified. Language to be included follows:

Data from this study will be submitted to the National Institute of Mental Health Data Archive (NDA) at the National Institutes of Health (NIH). NDA is a large database where deidentified study data from many NIH studies are stored and managed. Sharing your deidentified study data helps researchers learn new and important things about brain science more quickly than before.

Deidentified study data means that all personal information about you (such as name, address, birthdate and phone number) is removed and replaced with a code number. The study researchers will have to collect your personal information from you in order to make that code number. The code number cannot be used to identify you. The study researchers will never send your personal information to NDA.

10.10 Retention of Records

Study documents should be retained for a minimum of 2 years after the last approval of a marketing application in an International Conference on Harmonisation (ICH) region and until there are no pending or contemplated marketing applications in an ICH region or until at least 2 years have elapsed since the formal discontinuation of clinical development of the study intervention. These documents should be retained for a longer period, however, if required by local regulations. No records will be destroyed without the written consent of the sponsor, if applicable. It is the responsibility of the sponsor to inform the investigator when these documents no longer need to be retained. The company supplying the study medication (Novartis) will also be consulted on destruction of study materials.

10.11 Study Monitoring

Clinical site monitoring is conducted to ensure that the rights and well-being of trial participants are protected, that the reported trial data are accurate, complete, and verifiable, that the facilities and staffing are adequate for continued study conduct, and that the conduct of the trial is in compliance with the currently approved protocol/amendment(s), with International Council for Harmonisation Good Clinical Practice (ICH GCP), and with applicable regulatory requirement(s) including federal, state and local regulations and institutional policies and procedures.

Clinical site monitoring will be performed by the Yale Center for Clinical Investigation (YCCI). Monitoring visits will include a site initiation visit, regularly scheduled on-site interim monitoring visits and/ or remote interim monitoring visits while subjects are on study, and a site close-out visit at the site. Following each monitoring visit, a visit report will be generated containing information on site activities and a summary of pertinent points and action items. The report will be provided with a follow-up letter. Site-specific data status reports will be distributed to the site regularly to outline planned, missing or incomplete case report forms and any outstanding data gueries.

During monitoring visits, the following may be reviewed:

- Protection of the rights, safety and welfare of subjects through review of informed consent process and documentation, adverse events (AEs) and serious adverse events (SAEs) and safety procedures
- Subject eligibility
- Source verification
- Protocol compliance
- · Deviations and Non-compliance
- Investigator Site File
- ICH GCP compliance
- Investigational Drug/ Device Storage and Accountability (including quantity and disposal procedures)

- Laboratory Facilities
- Equipment maintenance and calibration
- · Additional study supplies inventory and assessment
- Study progress and/or follow-up on issues with Site Principal Investigator (PI) and relevant members of the study team

The Study PI and YCCI will define the required study monitoring activities in a Clinical Monitoring Plan (CMP). The CMP describes in detail who will conduct the monitoring, at what frequency monitoring will be done, at what level of detail monitoring will be performed, and the distribution of monitoring reports.

10.12 Data Safety Monitoring Plan

This protocol is a moderate risk protocol and therefore requires a data safety and monitoring plan.

The principal investigator will be responsible for monitoring the data, assuring protocol compliance, and conducting the safety reviews at the specified frequency, which must be conducted at a minimum of every 6 months (including when reapproval of the protocol is sought). During the review process, the principal investigator will evaluate whether the study should continue unchanged, require modification/amendment, or close to enrollment. Either the principal investigator, the IRB, Novartis, or the CTNA DSMB have the authority to stop or suspend the study or require modifications.

We will be accessing the Data and Safety Monitoring Board (DSMB) developed for the Center for Translational Neuroscience on Alcoholism ([name], PI) since this project is a component within this Center. The DSMB is multi-disciplinary and includes representatives with expertise in the primary components of the proposed trial. The following individuals will be on the DSMB as voting members:

[name], PhD., [name] (Brown)/ASOS Res Provid. VAMC Chmn, DSMB, [name]., Director, Decision Sci. Int., Statistician, DSMB, [name]., Dir, Dept Psychiatry Ethics Committee, IRB Rep, DSMB, [name]., [name], Fairfield Univ. Ethicist, DSMB

This DSMB will follow the operational guidelines outlined in the YCCI OR CNRU plan for DSMB. We hope to recruit subjects at a maximum rate of 5-10 per month, thus, the DSMB will review safety reports two times a year. More frequent meetings will be scheduled if indicated by interim findings.

10.13 Study Modification

All study modifications will be determined by the study PI. Modifications will be submitted to Yale HIC (IRB) for approval prior to being implemented. Upon approval from IRB, the Sponsor and FDA will be notified of all modifications.

10.14 Study Discontinuation

If the study is prematurely terminated or suspended, the Principal Investigator (PI) will promptly inform study participants, the Institutional Review Board (IRB), and sponsor and will provide the reason(s) for the termination or suspension. Study participants will be contacted, as applicable, and be informed of changes to study visit schedule.

Circumstances that may warrant termination or suspension include, but are not limited to:

- Determination of unexpected, significant, or unacceptable risk to participants
- Demonstration of efficacy that would warrant stopping
- Insufficient compliance to protocol requirements
- Data that are not sufficiently complete and/or evaluable
- Determination that the primary endpoint has been met

Determination of futility

10.15 Study Completion

The study PI and Sponsor will determine the completion of the study with regards to targets for enrollment and study completers. Upon completion, IRB (Yale HIC) and FDA will be notified appropriately.

10.16 Conflict of Interest Policy

The independence of this study from any actual or perceived influence, such as by the pharmaceutical industry, is critical. Therefore, any actual conflict of interest of persons who have a role in the design, conduct, analysis, publication, or any aspect of this trial will be disclosed and managed. Furthermore, persons who have a perceived conflict of interest will be required to have such conflicts managed in a way that is appropriate to their participation in the trial. The study leadership in conjunction with the appropriate conflict of interest review committee has established policies and procedures for all study group members to disclose all conflicts of interest and will establish a mechanism for the management of all reported dualities of interest.

All investigators will follow the applicable conflict of interest policies.

10.17 Funding Source

This study is being conducted as part of the Center for the Translational Neuroscience of Alcoholism (CTNA-5) which is funded by a grant from National Institute on Alcohol Abuse and Alcoholism / NIH / DHHS (#2P50AA012870-21).

10.18 Publication Plan

Any resulting publications will be done with approval of the PI, Sponsor, and Novartis.

11 Appendices

р	

APPROVED BY THE YALE UNIVERSITY IRB 11/22/2023

APPROVED BY THE YALE UNIVERSITY IRB 11/22/2023

TIME	START OF DRINKING SESSION PROCEDURES
Prior to	Confirm [name] signed off on EPIC orders
arrival	Confirm participant breakfast and lunch were ordered from HRU and transport was setup.
RA	Confirm covid questions were filled and negative rapid covid test and send both to [contact] and [contact] .
	Pick up study alcohol and meds from IDS
	Bring to lab: alcohol, participant binder, participant folder, CTNA laptop, fruit juice mixer and frozen breakfast option (if needed).
	Confirm participant was added to OnCore
8:15 am	*RA and participant to have a mask on in lab (confirm extra masks are at lab)
RA	Give participant meds (if first dose is scheduled for tomorrow)
	Meet participant in 1st floor lobby and walk them to the CSRU on the 4th floor
	Get study cart from OnCore/Epic Suite #404, code 9224#, Key holder (PIN 3636)
	Urine drug screen and pregnancy test (*RA to send urine to Quest): Neg Pos
	Record time of last drink Amount of last drink
	Instruct participant on using both (BAC and CO) step out of room.
	BAC Level: CO Level:
	*If BAC is positive, notify [name] [contact]
	Concurrent medications, TLFB, SAFTEE
	Collect subject's cigarettes (if applicable) Smoker: Nonsmoker:
	Height: inches (Shoes off) Weight: kgs lbs.
	*For data only. IDS will be using height and weight from PE for alcohol calculations.
	Fill out Quest form for today

	Baseline PACKET #1: YCS Long, AES, BAES, BIS, BIS/BAS, UPPS, SRHI, PROMIS Sleep
	and Impairment Measures, AUDIT-C, W9
	Baseline Assessments
	Body Sway Task (Confirm data is recording and showing weight, if not restart task)
	CPT
	SRT
	CRT
9:00 am	Give subject breakfast. Time: (Ensure they eat, so they don't have an empty stomach)
RA	*NO FOOD AFTER 10AM, UNTIL AFTER DRINKING SESSION IS OVER
11:00 am	Place heplock in non-dominant arm (DO NOT USE A RUNNING IV)
NURSE	*If you experience any problems or have any concerns with the IV placement, please contact study staff PRIOR to placing IV.
	Record actual time of blood draw:
	DRAW "-60min" BAL (blue microtube)
	Health Profile (CMP, CBC w/diff, TSH, Phosporous, Magnesium, Uric Acid)
	2 Marble/gold 5ml top tubes (spun) and 1 lavender tube 4ml (unspun) *RA to send samples Quest
	1 MAV lavender 10ml pre "-60" plasma level. Put two lables on tube. Process in cold centrifuge (-80 degrees freezer or dry ice)
	Urine (Urinalysis) *RA to send samples to Quest
11:00 am RA	Place labled Health Profile (2 Marble/gold 5ml top tubes (spun), 1 lavender tube 4ml
101	(unspun), and urine sample in Quest box on 4th floor outside of room 401.
	Call Quest for pickup or online (ensure they arrive prior to building closing)
	Record dose of alcohol from Pharmacist and mixer
	Alcohol Dose (vodka): ml Mixer (Juice): ml
	Bathroom break and ensure participant has water to drink.
	Premix all 6 drinks Juice (of their choice) and vodka (0.03 mg%) and cap securely.
	Keep drinks on ice.
	Setup Zoom on laptop to communicate during drinking session.

11:55 pm	Bring all 6 drinks into room with participant. Bring packets 2-7 into room.
RA	Set up for drinking session and READ study spiel to subject.
12:00 pm	Drink #1, Juice (of their choice) and vodka (0.03 mg %)
RA	Instruct participant that s/he has 15 minutes to drink cup #1 and to pace their drinking so it is consumed over the entire 15-minute period. (start timer count up)
12:15 pm NURSE	BP: Pulse: (BP cuff on arm opposite IV, stays on until the end of
None	the drinking session)
	DRAW "+15min" BAL Record actual time of blood draw:
12:15 pm	PACKET#2: YCS, AES
RA	Drink #2, Juice (of their choice) and vodka (0.03 mg %)
	Instruct participant that s/he has 15 minutes to drink it (start timer)
	BP: Pulse:
12:30 pm	DRAW "+30min" BAL Record actual time of blood draw:
NURSE	
12:30 pm	PACKET #3: YCS, AES
RA	Drink #3, Juice (of their choice) and vodka (0.03 mg %)
	Instruct participant that s/he has 15 minutes to drink it (start timer)
12:45 pm	BP: Pulse:
NURSE	DRAW "+45min" BAL Record actual time of blood draw:
12:45 pm	PACKET #4: YCS, AES, BAES
RA	Drink #4, Juice (of their choice) and vodka (0.03 mg %)
	Instruct participant that s/he has 15 minutes to drink it (start timer)
1:00 pm	BP: Pulse:
NURSE	DRAW "+60min" BAL Record actual time of blood draw:
1:00 pm	PACKET #5: YCS, AES
RA	Drink #5, Juice (of their choice) and vodka (0.03 mg %)
	Instruct participant that s/he has 15 minutes to drink it (start timer)
1:15 pm	BP: Pulse:
NURSE	DRAW "+75min" BAL Record actual time of blood draw:
1:15pm	PACKET #6: YCS, AES
RA	Drink #6, Juice (of their choice) and vodka (0.03 mg %)

	Instruct participant that s/he has 15 minutes to drink it (start timer)
1:30 pm	Have subject rinse mouth out with water
NURSE	Breath Alcohol Level: If above 0.02, repeat at 2pm
	DRAW "+90min" BAL Record actual time of blood draw:
1:30 pm	PACKET #7: YCS, AES, BAES
RA	Post Assessments
	Body Sway Task (confirm data is recording and showing weight, if not restart task)
	CPT
	SRT
	CRT
	Give participant snacks for after lunch
	Please wait until participant has finished current task before entering room
2:00 pm	BP: Pulse:
NURSE	DRAW "+120min" BAL Record actual time of blood draw:
	PACKET #8: YCS, AES
	Breath Alcohol Level:
	Serve participant Lunch
2:30 pm	Breath Alcohol Level: If above 0.02, repeat at 3:00pm
NURSE	PACKET #9: YCS, AES
	17.0KE1 #0. 100, NE0
3:00 pm	BP: Pulse:
NURSE	DRAW "+180min" BAL Record actual time of blood draw:
	PACKET #10: YCS, AES
	Breath Alcohol Level: If above 0.02, repeat at 3:30
3:30 pm	
NURSE	Breath Alcohol Level: If above 0.02, repeat at 4:00pm
4:00 pm	BP: Pulse:
NURSE	DRAW "+240min" BAL Record actual time of blood draw:
	Breath Alcohol Level: If above 0.02, repeat at 4:30pm
4:30 pm	BP: Pulse:

NURSE	Breath Alcohol Level: If above 0.02, repeat at 5:00pm
5:00 pm	BP: Pulse:
NURSE	DRAW "+300min" BAL Record actual time of blood draw:
	Remove IV catheter
	Breath Alcohol Level: If above 0.02, repeat at 5:30pm
	If below .02 please contact RA to arrange participant transportation home.
5:30 pm	BP: Pulse:
NURSE	Breath Alcohol Level: If above 0.02, repeat at 6:00pm
	If below .02 please contact RA to arrange participant transportation home.
6:00 pm	BP: Pulse:
NURSE	Breath Alcohol Level:
	Please contact RA to arrange participant transportation home.
6:00 pm	Confirm Quest picked up samples from Quest box on 4th floor outside of room 401.
RA	Check on all supplies (drugs tests, pregnancy tests, breathylzer tubes, CO tubes, etc). If any thing
	is low resupply.

12 References

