Alcohol may also cause nausea in high doses; however, nausea is not expected at the dose being used in this sample of healthy volunteers who will report prior experience of consuming alcohol levels similar to the quantity used in this study. Alcohol dosing will be calculated using published gender specific algorithms based on estimated body water determined from height, weight, and age and the amount of alcohol provided will raise their blood alcohol levels to 80 mg/dl which is the legal limit of intoxication to levels.

Another area of potential risk to subjects under the influence of alcohol involves their safety during the experimental procedures. Although impairment of gross motor coordination in these subjects may occur, all subjects will be under the supervision of the experimenters to prevent possible accidents such as falls. To ensure the safety of our subjects, they will be monitored until their BAC falls to below .02 or until 6pm. All participants will be provided with transportation to and from the lab sessions to ensure their saftey.

There is no data looking at the effects of alcohol with mavoglurant. However, this interaction is the purpose of this study and the amount of alcohol that will be given subjects is no more than the amount they may drink in a social environment.

Risks associated with urine collections:

Screening urine collections are performed primarily as safeguards to subjects and should add no risks other than those normally associated with these procedures. Subjects will have approximately 50cc of blood drawn at the PE appointment to determine liver and kidney functioning. We will draw approximately 70.5cc of blood during the first lab session and 85.5cc of blood at the second lab session for BALs and health profile and PK samples. The morning after lab session 2, 50cc's of blood is drawn. At the 1 week follow up 50cc will be drawn again for health profile. Therefore, the total amount of blood drawn during the study (306 ml) is well within the HIC guidelines of 450 cc within 8 research weeks, and the blood loss poses minimal risk in healthy subjects. We will advise subjects against donating blood for 6 weeks following study participation.

BLOOD DRAW	PE	DS1	DS2	Morning after	1 WEEK F/U
Chem Profile (safety labs) 50 cc/draw	х	Х	Х	Х	Х
BAL (total 11 vials/visit) 0.5 cc/draw (5.5/DS)		Х	Х	Х	
PK Assay		Х	Х		
15 cc/draw			(2)		

Risks associated with rating scales and questionnaires:

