8.1 General Design Description

Double blind placebo-controlled trial of mavoglurant vs. placebo in light social drinkers (i.e., consuming 1- 6 standard alcoholic drinks per week and having engaged in at least one and no more than 12 binge drinking episodes in the past year). Participants will not meet criteria for a DSM-V Alcohol Use Disorder and must be willing to abstain from alcohol during the outpatient medication treatment phase. We propose to recruit 40 male and female social drinkers (to achieve a completer sample of 28 participants).

Subjects will sign informed consent and eligibility will be determined. Eligible subjects will participate in two alcohol administration lab sessions. They will be randomized to receive either 200 mg/day of mavoglurant or placebo for 7-10 days (14 in each study arm). During the outpatient medication administration phase, subjects will be observed daily as their medication is administered. Adverse events will be assessed. The first lab session will occur on Day 0 (prior to start of study medication) and the second lab session will occur following 7-10 days (as scheduling permits) of study medication. During each lab session, subjects will receive six successive doses of alcohol over a 90-min period designed to raise their blood alcohol levels to 80 mg/dl. Outcomes will include adverse events (during outpatient period and the lab session), safety labs (before and after drug and after alcohol), PK/PD of drug and alcohol, behavioral tests of cognition and body sway as well as self-reports of intoxication and other alcohol effects. Study staff will check in with subjects on the two days following the second lab session and an in-person follow up appointment will be scheduled 1 week after the second lab session.

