See appendix for detailed procedure sheet. Participants will arrive at the Hospital Research Unit (HRU), Church Street Research Unit (CSRU), or Masonicare at 8:15am. We will collect BAC, urine toxicology, and conduct paper and pencil baseline questionnaires. At 9:00am,

participants will be provided breakfast. They will then complete additional study assessments. We will put an IV catheter in the participant's arm at 11:00am and we will draw the initial set of labs. At 12:00pm, participants will be given their first drink of 80-proof vodka with a non-carbonated mixer of their choice and will be instructed to drink it in 15 minutes. They will continue to receive successive doses of alcohol in 6 equal portions (every 15 minutes) over a 90-min period designed to raise their blood alcohol levels to 80 mg/dl: we chose this dose because this the legal limit of intoxication and is close to the peak BAC we have observed in prior ADP sessions (with approx. 200 heavy drinkers) and is similar to the alcohol dose used in a previously completed similar protocol with another drug (HIC #0602001068). Alcohol dosing will be calculated using published gender specific algorithms based on estimated body water determined from height, weight (obtained at physical exam), and age and translated into ml of 80-proof vodka (Curtain & Fairchild, 2003). Regardless of the amount of vodka required, the amount of mixer will be adjusted so that the total volume of fluid will be constant. These methods of alcohol administration have been safely used by our group (Jatlow, et al., 2014), with volunteers who had similar drinking profiles. At 12:15pm, a blood pressure cuff will be placed on his/her arm to monitor vitals throughout the lab session. Safety labs will be drawn and blood samples will be collected at regular intervals (at baseline and every 15 minutes during the lab session and then hourly for the next 3 hours) to assess blood alcohol levels and to assess Mavoglurant levels. They will complete paper and pencil questionnaires about mood, medication and alcohol effects at regular time intervals, as well as the Body Sway Task.

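### Does the unexplained 0.03 mg% on the drinking-session sheet conflict with the 80 mg/dl alcohol target in a way that affects the trial?

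*Combined protocol and SAP*

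**What the plan says.** The body of the protocol is consistent about the target. Section 6.1.1 says "the amount of alcohol provided will raise their blood alcohol levels to 80 mg/dl". Section 8.1 describes "six successive doses of alcohol over a 90-min period designed to raise their blood alcohol levels to 80 mg/dl". Section 9.3 gives the alcohol in "6 equal portions (every 15 minutes) over a 90-min period designed to raise their blood alcohol levels to 80 mg/dl", with the same target for both lab sessions.

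Section 9.3 also says how the amount is found: a sex-specific body-water calculation from height, weight and age, converted to ml of 80-proof vodka. The sheet agrees. It notes that "IDS will be using height and weight from PE for alcohol calculations", and it has staff record the pharmacist's figure on the line "Alcohol Dose (vodka): ml Mixer (Juice): ml".

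The unexplained figure sits beside these entries. It appears once at the premix step, "Premix all 6 drinks Juice (of their choice) and vodka (0.03 mg%) and cap securely", and then on every drink line, the first of which begins "Drink #1, Juice (of their choice) and vodka (0.03 mg" and continues with a percent sign. That is seven times in all. The figure 0.03 appears nowhere else in the documents.

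The visible sheet is the one for Lab Session 1, since its 8:15 am entry reads "Give participant meds (if first dose is scheduled for tomorrow". Section 8.1 places that session on Day 0, before study medication starts. Section 9.3 refers to an appendix sheet for Lab Session 2 as well, but none is visible in the text supplied.

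**The concern.** Staff mix the challenge drinks from this sheet, and section 9.3 sends the reader to it for the detailed procedure. Because mg% is the same unit as mg/dl, the printed number lies hundreds to thousands of times below the stated target if it is taken as a blood level. If a different unit was intended, the number still misses the target, and the per-drink reading misses it on the high side.

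If the label governed what was poured, alcohol exposure could differ from what the protocol describes. The blood alcohol comparison between sessions (section 9.5.1) would then rest on an uncertain dose. The Synopsis promises the same fixed alcohol dose at both sessions, so a label acted on at one session and not the other would also confound the session contrast.

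**Working it through.** **Inputs from the documents.** Label 0.03 mg% (section 11 sheet). Target 80 mg/dl (sections 6.1.1, 8.1 and 9.3). Six equal portions over 90 minutes, or 1.5 h (section 9.3). Level below .02 after about 4 hours (section 9.3).

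**Assumptions.** mg% = mg/dl. g% = 1,000 mg/dl. The .02 is on the g% scale, so 20 mg/dl. Elimination of 0 to 25 mg/dl per hour. 80-proof means 40% by volume. Ethanol density 0.789 g/ml (range 0.78 to 0.80).

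**Step 1: the label as a blood level.**

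| Reading | Calculation | Result | Against 80 mg/dl |
|---|---|---|---|
| mg%, session total | 0.03 | 0.03 mg/dl | 80 / 0.03 = about 2,667 times lower |
| mg%, per drink | 6 x 0.03 | 0.18 mg/dl | 80 / 0.18 = about 444 times lower |
| g%, session total | 0.03 x 1,000 | 30 mg/dl | 37.5% of target |
| g%, per drink, gross | 6 x 30 | 180 mg/dl | 225% of target |

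**Step 2: can elimination close the gap?** A fall from 80 to 20 mg/dl in 4 h implies (80 − 20) / 4 = 15 mg/dl per hour. Over 1.5 h that turns 180 into 180 − 22.5 = 157.5 mg/dl. The range for 0 to 25 mg/dl per hour is 180 down to 142.5. Bringing 180 to 80 would need (180 − 80) / 1.5 = 66.7 mg/dl per hour. Elimination does not explain the label.

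**Step 3: is it one portion's share of the target?** 80 / 6 = 13.3 mg/dl without elimination. At 15 mg/dl per hour it is (80 + 22.5) / 6 = 17.1 mg/dl. Neither 0.03 nor 30 mg/dl fits.

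**Step 4: is it the strength of the drink?** 80-proof vodka holds 0.40 x 0.789 x 100 = 31.56 g per 100 ml, or 31,560 mg/dl. Dividing by 0.03 gives a dilution of about 1.05 million-fold (1.04 to 1.07 million over the density range). That is not a vodka-and-juice drink.

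**Step 5: what sets the amount poured?** A concentration cannot be poured without a volume, and the sheet's only volume entry is the ml line filled in from the pharmacist. The sequence is body-water calculation, ml of vodka, pharmacy figure on the sheet, six equal portions. The label enters at no point.

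**Step 6: what enters the analysis?** Section 9.5.1 uses the area under the curve of measured blood alcohol. The sheet schedules draws at −60, +15, +30, +45, +60, +75, +90, +120, +180, +240 and +300 minutes. That is 11, which matches the 11 vials per visit in section 6.1.1. The label is not an input.

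**The case for a change.** The strongest opposing case is that the sheet belongs to the protocol and the slip is repeated on every drink line, so it is not an artefact of text extraction. The protocol moves between mg/dl (80) and a bare decimal scale (.02) for alcohol levels, which makes a unit mix-up easy. The ml line does not say whether it is the session total or one portion. Correcting a sheet costs almost nothing, and a study in heavy drinkers is meant to follow.

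Much of this stands. The label is undefined, no tested reading matches the target, and a unit slip is the likeliest explanation. One reading comes near: 0.03 g% per pair of drinks gives 3 x 30 = 90 mg/dl gross and 67.5 at 15 mg/dl per hour. It does not fit a label printed on every single drink.

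Three parts do not carry the point further:

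- **Contradiction.** A number with no stated meaning can be shown to contradict the target only once it is assumed to be a blood level.
- **Combined exposure.** The lack of data on alcohol with mavoglurant (section 6.1.1) does not bear on this sheet, because no participant has taken study drug at Lab Session 1.
- **The ml line.** This is a separate matter, and section 9.3 already says that the calculated dose is split into six equal portions.

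One reassurance must also be dropped. The 11 blood samples are stored and assayed later (section 9.2, item g), so they can verify exposure afterwards but do not limit it during drinking. The first breath reading listed after drinking starts is at 1:30 pm, after the sixth drink. The safeguard that holds is the pharmacy's volume in ml.

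**Conclusion.** This is a clerical slip with no statistical consequence. The seven 0.03 mg% entries are undefined. As blood levels they come to 0.03 or 0.18 mg/dl as printed, or 30 or 180 mg/dl gross on the g% scale, against 80 mg/dl. The shown effect on the delivered dose is none, because the volume comes from the pharmacy in ml. The shown effect on the blood alcohol comparison is none, because measured levels are analysed. No difference between arms or sessions is shown.

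The sheet and sections 6.1.1, 8.1 and 9.3 must be reconciled by those who maintain them, including on the Lab Session 2 sheet if it carries the same label. Which figure stands is not decided here. That is routine upkeep of a working sheet and would alter no design element, endpoint or analysis. The operational gain is also small: section 7.2 refers to 10 + 14 = 24 participants who had completed, of 28 intended.

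The conclusion rests on the poured volume following the ml entry, as section 9.3 and the sheet describe, and on nothing in the unseen Lab Session 2 sheet making the label a dosing instruction. The g% reading, elimination rates and ethanol density are assumptions, but no value in the ranges shown changes the result.
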